
 CCI [REDACTED] 	
 Collection of biospecimens unless prohibited by local regulations or ethics committee decision. Additional information on collection

	and potential use is provided in the Biospecimens section.
--	--

Overall Design

This is a Phase 1, randomized, double-blind, Sponsor-open, placebo-controlled, first-in-human SAD study to evaluate the safety, tolerability, and PK of PF-06755347 in healthy adult male participants by IV and SC administration and in adult male or female participants with persistent or chronic primary ITP by SC administration.

A schematic of the overall study design is provided in [Figure 1](#).

A total of approximately 75 healthy adult male participants are planned to be randomized to either receive PF-06755347 or placebo by IV or SC administration in a 3:1 allocation ratio. Emerging clinical data from the IV cohorts supporting the transition to SC dosing are summarized in the IB, Section 6. The cohorts planned in this study are listed in Table 4. If cohort numbers are expanded, then the total number of participants randomized will not exceed 87.

Table 4. Cohort Overview for IV and SC Administration

Cohort	Population	Optional	Number of Participants Dosed	SC Administration Number of Participants Planned
1 - 4	HP		16	
5	HP		4	
6	HP		5	
7	HP		4	
8	HP		8	
9	HP		8	
10	HP	X	In progress	8
11	HP	X	ND	8
12	Japanese	X	ND	4 - 8
13	ITP		ND	3 - 6
14	ITP		ND	3 - 6

For all cohorts, participants will be dosed sequentially, with a minimum of 72-hour safety data (96-hour for SC administration) for each participant being reviewed by the team before dosing the next participant. There will be a minimum interval of 96-hours for IV administration or 120-hours for SC administration between dosing of consecutive participants. Screening evaluation will occur within 56 days prior to dosing. Eligible participants who meet the entry criteria will be admitted on Day -1 and are required to stay overnight through completion of Day 8 evaluations. At the discretion of the study site, participants may be admitted on Day -2. Participants will return for outpatient visits through approximately Day 36 (≤ 1 mg/kg IV dose level) or Day 71 (> 1 mg/kg IV dose level and all

subcutaneous dose levels) for a total of approximately 5 or 10 weeks study participation, respectively from first dose to follow-up, excluding screening.

Dose Escalation and Study Stopping

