Clinical tolerability, safety, PK, CCI [REDACTED] data will be reviewed by a dose escalation subteam to establish whether each dose level is considered safe and well tolerated. These criteria may lead to a pause to evaluate participants at a given dose level, to repeat a dose, or to dose escalation. Unless a specific pause criterion is met, a review of all available safety, PK, cytokine and complement data will occur after each cohort has completed and dose escalation will proceed if the last dose was considered to be well tolerated. In the event of dosing pause, all available safety, cytokine, and complement data for the participants will be reviewed by the dose escalation subteam. The subteam should determine whether clinical signs and symptoms, including laboratory findings, associated with the pause criteria have resolved and whether it is safe to continue dosing.

Data Monitoring Committee:

This study will not use an external data monitoring committee. However, the dose escalation subteam will include an external Sponsor-independent safety reviewer.

Statistical Methods

No formal inferential statistics will be applied to the pharmacokinetic data.

The plasma concentration of PF-06755347 will be listed and summarized descriptively by nominal PK sampling time and treatment group. Individual participant, mean and median profiles of the plasma concentration time data will be plotted by treatment group using actual and nominal times, respectively. Mean and median profiles will be presented on both linear and log scales.

Baseline and change from baseline in cytokines and complement components will be summarized descriptively and plotted by dose.

Platelet counts for participants in the ITP Cohorts will be listed and summarized descriptively as absolute values and change from baseline.

[figure not shown]
Immunogenicity (anti-drug antibody [ADA]) results will be listed (including titers) and summarized by treatment group and time points. Participant level immune response will also be summarized by treatment. Effect of positive ADA on safety, PD and PK will be assessed, if appropriate.

CCI [REDACTED]

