2.1. Study Rationale

The current study is the first clinical trial with PF-06755347. It is designed to evaluate the safety, tolerability, PK and CCI following IV infusion and SC injection to healthy adult male participants and SC injection in adult male or female participants with persistent or chronic primary ITP.

Platelet count response in ITP is a robust, objective, validated biomarker for efficacy for IVIg. An increase in platelet count would be informative for the clinical development of PF-06755347 in ITP and CIDP. Participants with persistent and chronic primary ITP are chosen to ensure a low likelihood of spontaneous resolution of the platelet count. Participants with moderate to severe ITP ($30 - 75 \times 10^9$ platelet count) who have no acute need for therapy are selected to minimize undue risk to the participant (see IB, Section 6.2.1.1), including bleeding at the injection site.

PF-06755347 modulates the production of pro- and anti-inflammatory cytokines and the production of complement activation products in vitro and in nonclinical species. A maximum tolerated dose of 0.3 mg/kg by intravenous infusion has been identified, with Grades 1 and 2 CRS observed at higher doses of 0.7 and 1 mg/kg. No further IV dosing will occur. (see Investigator Brochure Section 6.2). Moving forward, the safety, tolerability, and PK of PF-06755347 will be assessed following SC administration.

In ITP, bleeding may occur due to low numbers of platelets, circulating cell fragments that clump together to form plugs in blood vessel injuries.

The study design with single escalating IV and SC doses of PF-06755347 is ongoing with review of safety, PK and CCI. To permit an unbiased assessment of safety, the administration of active PF-06755347 versus placebo in each healthy participant cohort will be double-blinded to site staff (except those involved in preparation of doses) and participants. All participants in the ITP cohorts will receive PF-06755347. To allow for real-time review of the safety, tolerability, PK and cytokine/complement data, a designated limited number of Sponsor colleagues will be unblinded, with careful measures exercised to limit degree of unblinding. Refer to [Section 9.9](#) for details. An independent and medically qualified reviewer, external to Sponsor and with authority to pause dose escalation to the subsequent cohort, will also be included as an unblinded member of the dose-escalation subteam.

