6.6. Dose Progression

The participants within each cohort will be dosed using a sequential dosing scheme. For all cohorts, a single participant will be dosed at a given time, followed by a minimum of 72-hour (for IV) and 96-hours (for SC) safety monitoring period. In total there will be a minimum of 96 hours between each IV participant dosed and 120 hours for each SC participant dosed.

The following rules will be applied when considering dosing of the next participant in the cohort.

Sequential dosing may **proceed** only if no adverse events are reported OR all of the following criteria are met:

1. Any pro-inflammatory events are < Grade 2 Per CTCAE criteria in [Appendix 9](#).
2. All other adverse events are deemed mild or moderate in severity, regardless of relatedness.
3. Any laboratory, ECG or vital sign changes are considered not clinically significant.
4. No other pause or stop criteria are met.
5. For participants with ITP, in addition to the above criteria, no participant has greater than a 30% decrease in platelet count – defined from the immediate pre-dosing platelet count to the lowest postdosing platelet count. Dose progression will be independent of dose progression from HP cohorts at higher dose levels.

Sequential dosing should be **paused** if any criterion below is met in a participant receiving active drug:

1. Grade 2 (Objective) pro-inflammatory event (vomiting, diarrhea, hypotension or hypoxia) (see [Appendix 9](#)).
2. Adverse event which is considered to be severe (Grade 3 or higher) AND is deemed related to study intervention.
3. A moderate event (Grade 2) AND is deemed related to study intervention not otherwise identified as a proinflammatory event or AE of special interest, that in the opinion of the PI and Sponsor are of concern and warrant further investigation before additional dosing.
4. For participants with ITP, platelet count of <30 x 10⁹/L AND a decrease from baseline ≥30%, or a platelet count decrease from baseline of ≥50%, defined from the immediate pre-dosing platelet count to the lowest post-dosing platelet count, or a bleeding or bruising-related AE CTCAE 4.03 Grade 2 or higher (except metrorrhagia Grade 3 or higher).

Sequential dosing should be **stopped** at the current dose level if any criterion below is met in participant receiving active drug:

1. Grade 3 or greater pro-inflammatory event.
2. Serious adverse event that is deemed related to study intervention.

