3. A single occurrence of confirmed drug induced liver injury (see [Appendix 6](#)) or confirmed drug induced kidney injury (see [Section 7.1](#)) will be reported as a serious adverse event, and therefore, will be considered dose limiting.

In the event of a dose **pause**, all available safety, PK (if available), cytokine, and complement data for the participants will be reviewed by the dose escalation subteam. The subteam should determine whether clinical symptoms associated with the pause criteria have resolved and determine whether IL-6 has returned to near baseline levels ie that the event is reversible. IL-6 has been selected as the surrogate marker for decision making purposes as it appears to be the most sensitive cytokine pathways from the non-human primate and human in vitro data. However, TNF- α , IFN- γ cytokine and complement data will be available at the time of review. If the dose escalation subteam determines that dosing may resume, a plan that mitigates risks to participants with the resumption of dosing may be implemented. Such a plan could include a revision of inclusion/exclusion criteria, repeating or reducing the dose, reducing infusion/dosing rate or adding appropriate safety monitoring or prophylactic treatment. This mitigation plan may need to be discussed with the Institutional Review Board (IRB) or Regulatory Authority as appropriate. The ultimate decision to continue dosing of study participants rests with the PI. Sponsor dose escalation subteam cannot overrule PI decision/clinical judgement.

If the decision is to **stop** dose progression this will also stop any further dose escalation.

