6.7. Dose Escalation

After each cohort has completed, a batched level review of all available safety, PK, cytokine and complement data will occur. For purposes of dose escalation, a completer is defined as a participant that has finished the clinical confinement up to Day 8. Dose escalation can proceed if the last dose was considered to be safe and well tolerated in all participants up to Day 8. Dose escalation may be stopped if it is determined that the limits of safety and/or tolerability or PK stopping criteria have been reached. This decision will be made after a discussion takes place between the Sponsor study team and each site's investigator or delegate. The Sponsor study team may not overrule the investigators decision to stop dose escalation. If dose escalation is stopped because of any of these criteria, additional cohorts may receive the same or lower doses of the investigational product.

Dose escalation may **progress** when one of the following criterion is met:

- Sequential dosing was completed successfully for the cohort and the last dose was considered to be safe and well tolerated.
- In the event that a dosing pause criteria has been met for the cohort (see [Section 6.6](#)), the dose escalation subteam confirmed that, after review of all data, it is safe to progress. Any requested mitigations must be applied eg, reduction in infusion rate.
- Dose escalation from the first to second ITP cohort will occur when the first dose is deemed safe and tolerable in ITP participants AND the second ITP cohort dose is deemed safe and tolerable in HPs, ie, dependent upon HP data.

For sites in the Czech Republic, the participation of females with ITP should commence only following approval by the Sponsor's dose escalation subteam. Please refer to [Appendix 12: Country Specific Requirements](#) for further details.

The dose escalation will be **terminated** if any of the following criterion is met:

- If 50% or more of the participants receiving active drug at a given dose level (but not participants receiving placebo) develop similar clinically significant laboratory, ECG, or vital sign abnormalities, in the same organ class, indicating dose-limiting intolerance.
- Severe nonserious AEs, considered as, at least, possibly related to study intervention administration, in 2 participants at a given dose level (but not participants receiving placebo), independent of within or not within the same system organ class, indicating dose limiting intolerance.

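### After a dosing pause, Section 6.6 implies that subteam and PI must both agree to resume, but its closing sentences, read literally, let the PI resume against a negative subteam finding

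*Protocol*

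**What the plan says.** Section 6.6 of the protocol governs the dosing of the next participant in a cohort. Three parts of it matter here.

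- **Proceed rule.** Dosing goes on only when no adverse event has been reported or when every item on a list is satisfied. One item is that no other pause or stop criterion has been met.
- **Pause rule.** Dosing pauses "if any criterion below is met in a participant receiving active drug". The criteria include Grade 2 hypotension or hypoxia, a related event of Grade 3 or higher and, in ITP, a platelet fall of 50% or more.
- **After a pause.** The subteam reviews safety, cytokine, complement and any available PK data. It judges whether symptoms have resolved and IL-6 is back near baseline. The text continues "If the dose escalation subteam determines that dosing may resume", in which case a mitigation plan may follow. The paragraph closes: "The ultimate decision to continue dosing of study participants rests with the PI. Sponsor dose escalation subteam cannot overrule PI decision/clinical judgement".

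The Synopsis (Section 1.1) asks the subteam to judge whether the findings "associated with the pause criteria have resolved and whether it is safe to continue dosing". For escalation to the next dose, Section 6.7 says: "The Sponsor study team may not overrule the investigators decision to stop dose escalation".

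In the healthy-participant cohorts the site staff are blinded (Section 6.3.2). The unblinded reviews go to a limited group of sponsor colleagues and an independent safety reviewer (Section 9.9). The ITP cohorts are open-label (Section 6.1.1).

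**The concern.** A pause rule has to be clear at the moment when the people applying it disagree. Section 6.6 sets out what happens if the subteam clears resumption but has no branch for the case where it does not. The only sentences that speak to a disagreement are the closing two, and they favour the PI in both directions.

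Protecting a PI who refuses to dose is sound. Protecting a PI who wishes to continue against the advice of the reviewing group is not, and nothing in the protocol suggests that this was wanted. At stake is dosing of a further participant at the same level in a first-in-human trial that has already seen Grade 1 and 2 cytokine release syndrome with IV dosing (Section 2.1). In the healthy-participant cohorts the literal rule would also put the last word with the blinded party, while the subteam holds the unblinded data.

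**Working it through.** No arithmetic applies. The check sets the provisions side by side.

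1. **Is subteam clearance needed after a pause?** By implication, yes. Once a pause criterion is met, the proceed rule is no longer satisfied. The only route to resumption that Section 6.6 describes runs through the subteam's determination. The Synopsis agrees, since it gives the subteam the question of whether continuing is safe.

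2. **What if the subteam's finding is negative?** No sentence says that dosing then stays paused. Of the two closing sentences, the first names a decision to continue. The second covers any PI decision and is not limited to a decision to stop.

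3. **How does Section 6.7 treat the same issue?** It differs in two ways. Its bar on overruling covers only a decision to stop. For a cohort that has paused, it lists subteam confirmation of safety as a criterion for escalating and makes requested mitigations compulsory. Section 6.6 has no matching criterion for resuming within the cohort, and its mitigation plan is optional.

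4. **Does other text resolve a disagreement on resumption?**
 - The external reviewer is described in Section 2.1 as "with authority to pause dose escalation to the subsequent cohort, will also be included as an unblinded member of the dose-escalation subteam". That authority concerns escalation, not resumption within a cohort.
 - The Synopsis has 72-hour data (96-hour for SC) "for each participant being reviewed by the team before dosing the next participant". Neither it nor Section 4.1 says who decides if views differ.
 - Section 6.1.1.2 keeps the whole cohort paused after any serious adverse event on active treatment until the PI and sponsor have both assessed causality. This covers serious events only.
 - Section 10.1.7 lets the sponsor close a site or end the study at its sole discretion. That is an effective backstop, but not a rule on resumption.
 - The SAP says that no decision rules are required (its Section 4.2) and does not deal with pauses.

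5. **Which events remain exposed?** The stop criteria in Section 6.6 take out pro-inflammatory events of Grade 3 or higher, related serious adverse events, and confirmed drug-induced liver or kidney injury. Section 6.7 takes out escalation. What remains is resumption at the same dose level after a non-serious pause event.

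6. **Who holds the information?** The pause criteria count only participants on active drug, so triggering a pause in a healthy-participant cohort already depends on unblinded input. Under the literal closing sentences, the blinded PI would still have the final say on resuming. This step does not apply to the ITP cohorts.

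**The case against.** The strongest answer is that the closing sentences must be read in sequence. The paragraph runs from subteam review to subteam determination, then to a mitigation plan, possible discussion with the IRB or regulator, and last the PI. On that reading the PI's decision is the final step of several, and the bar on overruling stops the subteam from forcing a PI to dose. A subteam that withholds clearance overrules nothing, because the process has not reached the PI. The proceed rule supports this, and Section 8 allows no protocol waivers. A blinded PI who can only add a further refusal is a conservative arrangement.

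Most of this stands. It makes the two-key reading the likely intent. A reader might infer from the closing sentences alone that the subteam is merely advisory, or that nothing else restrains a PI who wants to resume. The documents do not support either inference: the proceed rule closes the gate, and the sponsor can close that PI's site.

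It does not cure the wording. The paragraph that reopens the gate is the same one that ends by giving the PI a final say on continuing that the subteam cannot overrule. The two-key rule has to be inferred against the literal text.

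**Conclusion.** The point holds in a narrow form. Section 6.6 contains two rules that conflict when the subteam's finding is negative and the PI wishes to continue. Its structure implies two keys, while its closing sentences literally allow one.

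The conflict matters only for resumption within a cohort, after a non-serious pause event, in a disagreement that stays unresolved and in which the sponsor does not use its right to close the site. That is a low-probability chain. The documents give no basis for a figure. A reader might try to size the gap by counting the participants still to be dosed when a pause occurs, but that reflects cohort size and does not measure the defect.

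This is a minor correction to a safety rule. It does not show that participants are generally unprotected after a pause, and it touches no endpoint, sample size or analysis. The conclusion rests on the protocol text alone. A Data Blinding Plan is mentioned in Section 9.9 but is not among the documents. The rule is still live: Table 4 shows Cohort 10 in progress and Cohorts 11 to 14 not yet dosed.

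**What to change.** Replace the two closing sentences of the pause paragraph in Section 6.6 with:

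> After a pause, dosing within the cohort resumes only if the dose escalation subteam determines that it may resume and the PI agrees; the subteam may not overrule a PI decision not to continue.

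This states the likely intent and brings Section 6.6 into line with the one-directional protection in Section 6.7. The PI keeps an absolute right to refuse. The cost is one sentence in the next amendment, and some pauses may last longer because both parties must agree before dosing resumes.

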6.7. Dose Escalation

After each cohort has completed, a batched level review of all available safety, PK, cytokine and complement data will occur. For purposes of dose escalation, a completer is defined as a participant that has finished the clinical confinement up to Day 8. Dose escalation can proceed if the last dose was considered to be safe and well tolerated in all participants up to Day 8. Dose escalation may be stopped if it is determined that the limits of safety and/or tolerability or PK stopping criteria have been reached. This decision will be made after a discussion takes place between the Sponsor study team and each site's investigator or delegate. The Sponsor study team may not overrule the investigators decision to stop dose escalation. If dose escalation is stopped because of any of these criteria, additional cohorts may receive the same or lower doses of the investigational product.

Dose escalation may **progress** when one of the following criterion is met:

- Sequential dosing was completed successfully for the cohort and the last dose was considered to be safe and well tolerated.
- In the event that a dosing pause criteria has been met for the cohort (see [Section 6.6](#)), the dose escalation subteam confirmed that, after review of all data, it is safe to progress. Any requested mitigations must be applied eg, reduction in infusion rate.
- Dose escalation from the first to second ITP cohort will occur when the first dose is deemed safe and tolerable in ITP participants AND the second ITP cohort dose is deemed safe and tolerable in HPs, ie, dependent upon HP data.

For sites in the Czech Republic, the participation of females with ITP should commence only following approval by the Sponsor's dose escalation subteam. Please refer to [Appendix 12: Country Specific Requirements](#) for further details.

The dose escalation will be **terminated** if any of the following criterion is met:

- If 50% or more of the participants receiving active drug at a given dose level (but not participants receiving placebo) develop similar clinically significant laboratory, ECG, or vital sign abnormalities, in the same organ class, indicating dose-limiting intolerance.
- Severe nonserious AEs, considered as, at least, possibly related to study intervention administration, in 2 participants at a given dose level (but not participants receiving placebo), independent of within or not within the same system organ class, indicating dose limiting intolerance.
- It is determined that the limit of safety and/or tolerability has been reached. This decision will be made following discussions between the study team and the investigator.
- Other findings that, at the discretion of the study team and investigators, indicate that dose escalation should be halted.
- Sequential dosing was stopped based on the criteria in [Section 6.6](#).
- At any dose level, the exposure reaches or exceeds the PK stopping limits in any individual participant (AUC_{168} of 34000 $\mu\text{g}\cdot\text{hr}/\text{mL}$ and/or C_{max} of 1130 $\mu\text{g}/\text{mL}$).
- Based on the observed data, the C_{max} or AUC_{168} of the next planned dose is projected to exceed the escalation limits in any individual participant, that dose will not be explored. Modified doses may be explored if they are not expected to exceed PK stopping criteria.

If following an internal safety review, it is appropriate to restart the trial, a substantial amendment will be submitted to CAs and ECs. The trial will not restart until the amendment has been approved by CAs and ECs.

Progression to the next dose will occur if the last dose was well tolerated and after satisfactory review of the available safety and PK data.

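### Section 6.7 lets further cohorts receive the same dose after a safety or tolerability stop without excluding a dose level that Section 6.6 has closed

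*Protocol*

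**What the plan says.** Section 6.6 of the protocol governs the step from one participant to the next: "The following rules will be applied when considering dosing of the next participant in the cohort". It has two adverse outcomes.

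- **Pause.** The dose escalation subteam may let dosing resume under a mitigation plan. "Such a plan could include a revision of inclusion/exclusion criteria, repeating or reducing the dose" is how the section lists some of the options.
- **Stop.** Dosing is to cease "at the current dose level if any criterion below is met in participant receiving active drug". The triggers are a pro-inflammatory event of Grade 3 or above, a related serious adverse event (SAE), or a confirmed drug-induced liver or kidney injury. The organ injuries, the section adds, "will be reported as a serious adverse event, and therefore, will be considered dose limiting". If progression is stopped, "this will also stop any further dose escalation".

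The opening paragraph of Section 6.7 says escalation may be stopped when a safety or tolerability limit, or a PK criterion, has been reached. After such a stop, "additional cohorts may receive the same or lower doses of the investigational product". The list of termination criteria later in 6.7 gives a 6.6 stop its own entry. A clause near the end requires an approved substantial amendment before the trial restarts, but does not say which stops bring it into play.

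For ITP, 6.6 says "Dose progression will be independent of dose progression from HP cohorts at higher dose levels". Section 6.7 says "Dose escalation from the first to second ITP cohort will occur when the first dose is deemed safe and tolerable in ITP participants", provided also that the second dose has been judged safe and tolerable in HPs.

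**The concern.** These are working stopping rules in a first-in-human trial, and someone will have to apply them soon after a serious event. Section 6.6 treats a stop as more severe than a pause and attaches no repeat option to it. Section 6.7 then gives a general permission to use the same dose again, with no exception for a level that 6.6 has closed. A team that wanted another HP cohort at that level could cite 6.7, and a team that did not could cite 6.6.

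Same-dose repeats are not improper in themselves. Section 4.2.1.3.1 describes an expansion cohort at 1 mg/kg IV, infused over 3 hours, after cytokine elevation at that dose. The protocol should therefore say when a repeat is allowed and when it is not.

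**Working it through.** No arithmetic applies. The check sets the rules side by side and follows one event through them.

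**1. What each section allows after each outcome**

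| Outcome | Section 6.6 | Section 6.7, opening paragraph |
|---|---|---|
| Pause | Resume, repeat or reduce under a mitigation plan | Not addressed there; a later bullet lets escalation progress if the subteam confirms it is safe |
| 6.6 stop | Dosing ends at that level and escalation ends; no repeat option given | Not named and not excluded |
| Safety, tolerability or PK limit | Not addressed as such | Same or lower doses permitted |

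**2. Does the 6.7 permission reach a 6.6 stop?** The permission refers back to the criteria just named, which are safety or tolerability limits and PK. A 6.6 stop is not named. But a related SAE, or an organ injury that 6.6 itself calls dose limiting, falls naturally under a safety limit, and nothing in the paragraph carves it out.

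**3. Does other text close the route?**

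- Section 4.1 allows doses in the sequence to be repeated or adjusted in light of results, without mentioning 6.6.
- Section 4.2.1.3.1 and note a to Table 7 make dose adjustments subject to 6.6 and 6.7. This sends the reader back to the same two sections.
- Section 6.1.1.2 pauses the cohort after any SAE on active drug, but only until causality has been assessed.
- The restart clause in 6.7 concerns restarting the trial. A 6.6 stop acts on a dose level and on escalation, and the clause does not say that it applies.
- Section 2.1 gives the external reviewer authority to pause escalation to the next cohort. It does not mention a same-dose repeat.

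Several of these favour caution, but none is an express bar.

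**4. Who could be affected?**

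- Cohort 12 receives the highest dose from Cohorts 7 to 11 found safe and well tolerated (Section 4.2.1.3.2).
- The ITP starting dose depends on the equivalent HP dose having been found safe (Section 4.2.1.3.3).
- The second ITP dose must be safe in HPs (Section 6.7).

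That leaves a repeat or added non-Japanese HP cohort.

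**5. Trace of the main point.** Suppose a related SAE occurs in an HP on active drug at 200 mg SC. Under 6.6, dosing at 200 mg stops and escalation ends. Under 6.7, escalation is terminated. Whether a further HP cohort may then receive 200 mg depends on whether the 6.7 permission is read to cover this stop. The text does not decide.

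**6. Trace of the secondary point.** Take the same HP stop at 200 mg, with the first ITP cohort at 25 mg and 50 mg already judged safe in HPs. The ITP doses listed are 25, 50 and 100 mg (Section 4.2.1.3.3), and HP levels of 200 and 300 mg are planned (Section 4.2.1.3.2). The closing line of 6.6 and the termination list in 6.7 name no population. Read literally, they block ITP escalation. The ITP bullet in 6.7, read alone, allows it once its two conditions are met. The independence sentence in 6.6 points to the intent, but it speaks of progression, which 6.6 uses for the next participant within a cohort.

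**The case against.** The strongest reply concerns what the 6.7 permission refers to. Its nearest reference is to safety or tolerability limits and PK. The termination list gives those and a 6.6 stop as separate entries, which suggests that the protocol treats a 6.6 stop as its own category. A permissive sentence also does not readily displace a specific rule that dosing stops at a level. The subteam must judge whether each dose level is safe, and the sponsor may not overrule an investigator's decision to stop escalation.

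Much of this stands. A reader might infer that 6.7 authorises re-dosing after a related SAE, or that the two sections flatly contradict each other. The documents do not support either reading, because 6.7 does not name a 6.6 stop. A reader might also take the 1 mg/kg expansion as a precedent for repeating a closed dose. The documents do not say that a 6.6 stop had been met there, and IV dosing has ended.

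What the reply does not supply is a sentence excluding a closed level from the same-dose permission. Separate entries in a list are an argument about intent, and oversight does not say which rule governs.

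**Conclusion.** The concern holds in a limited form. Section 6.6 closes a level after a stop and mentions a repeat only after a pause. Section 6.7 permits the same dose after a safety or tolerability stop and does not exclude a level closed under 6.6. The conclusion rests on reading a 6.6 stop as a kind of safety limit, which is natural but not explicit. The exposure is one type of cohort, a repeat or added non-Japanese HP cohort. The documents give no basis for a participant count. The gap is small, but it concerns participant safety and is cheap to close.

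The ITP question is a clarification only. A reader might infer that 6.6 and 6.7 disagree on whether an HP stop ends ITP escalation. They do not: both say that a 6.6 stop ends escalation. The tension is between that population-neutral wording and the specific ITP bullet in 6.7. A reader might also infer that the looser reading would open the second ITP cohort without any review of the HP event. That goes too far. Section 6.7 requires a review of all available safety, PK, cytokine and complement data after each cohort, makes the second ITP dose depend on HP data, and requires a satisfactory safety and PK review before the next dose. The strict reading carries no added safety risk; its cost is Cohort 14 (3 to 6 participants planned, Table 4). How far an HP stop should reach is a policy choice for the sponsor.

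**What to change.** **Main change, one sentence in the opening paragraph of 6.7:** *A dose level closed by a stop under Section 6.6 may not be given to any further cohort; only lower doses may be used, unless a substantial amendment allowing it has been approved under the restart clause of this section.*

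Leave the pause route in 6.6 as it is. Do not add an express permission to repeat the same dose after a PK stop or after a termination for dose-limiting intolerance. A PK stop can mean that a participant has reached the limits set from the monkey NOAEL, so the new sentence should not endorse that dose by implication.

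**Secondary clarification:** state whether an HP stop above the ITP dose range also ends ITP escalation, or whether the ITP bullet in 6.7 governs.

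**Cost:** two short wording changes, with no new data, participants or procedures. The sponsor gives up the option of a same-dose repeat after a 6.6 stop without an amendment.
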